3.1.5 Strata and Covariates

Randomization will be stratified by

. If there are

discrepancies in stratification factor values between the IRT and the EDC database, the values recorded in the EDC database will be used for all the analyses in this SAP. For deriving cidofovir use within 4 weeks prior to screening or during the screening process, such medication is taken within 4 weeks prior to screening visit through the randomization date.

3.1.6 Summary Statistics

Summary statistics will be presented by treatment group. Unless otherwise stated, continuous variables will be summarized using the number of non-missing observations, arithmetic mean, standard deviation, median, minimum, and maximum values as descriptive statistics. Categorical variables will be summarized using the frequency count and the percentage of participants in each category as descriptive statistics.

3.1.7 Handling of Missing Data

In general, data will be analyzed and presented as observed and will not be imputed for the analysis of efficacy and safety.

In case the start and end dates for adverse events (AEs) and concomitant medications/procedures are missing or incomplete, the missing component(s) will be assumed as the most conservative value possible. For example, AEs with missing start dates, but with stop dates either overlapping into the treatment period or missing, will be counted as treatment-emergent, taking the worst-case approach. When partial dates are present in the data, both a partial start date and/or a partial stop date will be evaluated to determine whether it can be conclusively established that the AE started prior to the start of study treatment or ended prior to the start of study treatment. If the above cannot be conclusively established based on the partial and/or present dates, then the AE will be considered as treatment emergent. Actual data values as they appear in the original case report forms (CRFs) will be presented in the data listings.

3.1.8 Handling of Contaminated Data

In general, viral load data from the central laboratory will be used for efficacy analyses If evidence can be provided for the contamination of central lab sample as "questionable integrity" or "questionable sample integrity", local laboratory viral load data will be used in place of the contaminated central laboratory sample.

3.1.9 Data Collected After End of Study

Data collected after the end of study will not be included in the summary tables but will only be presented in listings.

3.2 Analysis Populations

3.2.1 Intent-to-Treat (ITT) Population

The Intent-to-Treat (ITT) Population will include all randomized participants regardless of whether they are dosed or not. Participants will be analyzed according to the randomized study treatment.

3.2.2 BK Intent-to-Treat Population

The BK ITT Population will include participants in the ITT Population who have BKV detected in the urine. The primary efficacy analysis will be based on the BK ITT Population. In the BK ITT Population definition, BKV identification is determined based on the last available BKV urine viral load test result on or before the randomization date from central laboratory data or if central laboratory data are missing or have "questionable integrity" or "questionable sample integrity," from local laboratory data.

3.2.3 Modified ITT Population

The modified Intent-to-Treat (mITT) Population will include all randomized participants who receive any dose of study drug.

3.2.4 BK Modified Intent-to-Treat Population

The BK mITT Population will include participants in the BK ITT Population who receive any dose of study drug.

3.2.5 BK Per-Protocol Population

The BK Per-Protocol (PP) Population will include all participants in the BK mITT Population who do not have any major protocol deviations deemed to impact the results. Factors potentially impacting the primary efficacy result may include but are not limited to:

- Participants had major inclusion or exclusion violations
- Participants received the wrong study treatment (ie, did not receive the randomized study treatment assigned by the interactive responsive technology [IRT] system)
- Participants had low study drug compliance (<80%)
- Participants took a restricted concomitant medication
- Participants failed to complete the primary efficacy assessment
- Participants who did not have a Bedi Grade \geq 2 at randomization

The list of participants to be excluded from the BK PP Population will be finalized before database lock.

3.2.6 Safety Population

The Safety Population will include all participants who receive any amount of PSL or placebo. All safety analyses will be based on the Safety Population. Participants will be analyzed according to the treatment actually received.

3.3 Participant Data and Study Conduct

3.3.1 Participant Disposition

The number and percentages of participants who were screened and failed to meet eligibility criteria at screening will be summarized. The numbers and percentages of participants who were randomized, treated, discontinued early from study drug and study, and completed the study drug and study will be summarized by treatment group and in total based on the ITT population. Reasons for early discontinuation will also be summarized.

The numbers and percentages of participants in each analysis population will be summarized by treatment group and in total based on the ITT population. Reasons for exclusion from each analysis population will also be summarized.

3.3.2 Protocol Deviations

The numbers and percentages of participants with important protocol deviations by deviation category will be summarized by treatment group and in total based on the ITT population. Important protocol deviations related to the COVID-19 pandemic will be summarized by treatment group and listed based on the ITT population.

3.3.3 Demographic and Baseline Characteristics

The following demographic and baseline characteristics will be summarized, but not limited to:

- Age (years) and age group (<12 or ≥12 years; <18 or ≥18 years; <65 or ≥65 years)
- Use of cidofovir within 4 weeks prior to screening or during the screening process
- Sex
- Childbearing potential

- Race
- Ethnicity
- Height (cm)
- Weight (kg)
- Body mass index (BMI) (kg/m²) and BMI group (<30 kg/m², ≥30 kg/m²)
- Primary malignancy/underlying disease for transplant
- Type of transplant
- Participant CMV serostatus
- Blood Type
- Rh Factor
- HLA alleles from the study participant, the allogeneic HCT donor(s), and the VST donor(s) as well as the number of shared alleles among these individuals
- Baseline viral load in plasma (for BKV, AdV, CMV, HHV-6, JCV) or peripheral blood mononuclear cells (PBMCs; for EBV) for all target viruses
- Baseline viral load in urine for all target viruses
- Receipt of donor lymphocyte infusion >21 days prior to randomization

Demographic and baseline characteristics will be summarized with descriptive statistics or counts and percentages of participants as appropriate by treatment group and in total for all analysis populations.

3.3.4 Medical History

Medical history will be coded to system organ class and preferred term using the Medical Dictionary for Regulatory Activities (MedDRA). The numbers and percentages of participants with medical history by system organ class and preferred term will be summarized by treatment group and in total based on the safety population.

3.3.5 Prior and Concomitant Medications

Prior and Concomitant medications will be collected starting 30 days before screening and coded to anatomical therapeutic chemical (ATC Level 2) class and preferred term using the WHODrug Dictionary. All medications taken prior to the first dose of study treatment will be considered as prior medications. The medications taken prior to the first dose of study treatment and were ongoing or started on or after the first dose of study treatment will be considered as concomitant medications.

The numbers and percentages of participants taking prior and concomitant medications by ATC class and preferred term will be summarized by treatment group and in total based on the Safety Population.

3.3.6 Study Drug Exposure and Compliance

The number of doses and total dosing (including but not limited to prepared volume, total volume administered and duration of study drug infusion) will be summarized based on the safety population. The number of patients in the active treatment group who received two doses of the same PSL line versus two different PSL lines will be specified.

The length of exposure to study drug will be calculated as the number of days from the first dose of study drug to the last dose of study drug as:

Date of last dose - date of first dose + 14

Length of exposure will be summarized using descriptive statistics for the safety population.

A by-participant listing will be provided for study drug exposure.

Overall compliance will be calculated as:

(Sum of total volume administrated)/ (total volume planned)*100

The number and percentage of participants will be summarized for the safety population for the following categories for overall compliance: 0 - 80% and > 80%.

3.4 Efficacy Analyses

3.4.1 Primary Efficacy Endpoint

The primary endpoint is the time to resolution of macroscopic hematuria in participants with documented BK viruria. Resolution of macroscopic hematuria is defined as resolution to Grade 0 or 1 on the Bedi scale on 2 consecutive urine assessments \geq 2 days apart without continuous bladder irrigation or nephrostomy tubes that are uncapped; Grade 1 requires confirmation of resolution by urinalysis results of \leq 100 RBCs/HPF. If a participant has nephrostomy tubes that are capped, Bedi assessments may be performed on urine voided through the urethra or a bladder catheter (eg, Foley or suprapubic catheter), including for the purpose of assessing for resolution.

If the Bedi grade at randomization is missing, then the most recent screening Bedi grade will be used if available. If there are no Bedi grades at either randomization or during screening, the participant will be assumed to be eligible. The primary efficacy analysis will be conducted after all participants have completed 24 weeks of follow up or discontinued from the study. At the primary analysis, the PSL group will be compared to the placebo group in the BK ITT Population using a stratified log-rank test adjusting for stratification factors at randomization (derived based on EDC data). The study will be considered a success if the one-sided p-value from the stratified log rank test comparing treatment to control is less than 0.025. A stratified Cox proportional hazards model will be conducted to produce the hazard ratio of the treatment effect.

Time to resolution will be calculated starting from the date of randomization to the date of the first visual urine assessment without macroscopic hematuria (by the Hemostick® visual scale with score of 0 for outpatients; by the Bedi scale with a Grade 0 or 1 for inpatients) will be used, but 2 consecutive Bedi grades of 0 or 1 are required to establish resolution as noted above. If an outpatient does not have a Hemostick score at the time of resolution, the first of the 2 consecutive Bedi grades of 0 or 1 will be used for determining the time to resolution, which is the same approach being applied to inpatients. For inpatients who resolve on the date of hospital discharge, the Bedi grade scored on the discharge date will be used for determining time to resolution if available; if no Bedi grade is available at the time of discharge, then the Hemostick score will be used.

Participants not observed to achieve resolution will be considered censored at their last study follow up. Definitive therapies to stop bladder bleeding, such as cystectomy, bladder vessel embolization, cauterization, fulguration, or formalin instillation are permitted. If it is given before or on the day of randomization, the participant will be included in the BK ITT analysis assuming a Bedi of 2 or above. If it is given post randomization, it will be considered treatment failure for the primary endpoint of time to resolution of macroscopic hematuria and will be censored at the last follow-up time of any participant. Participants who discontinued early from the study before

achieving resolution will be censored at the time of last follow up. Participants who died or took non-PSL VSTs prior to reaching resolution will be considered treatment failures and censored at the last follow-up time of any participant.

For Bedi assessments where the grade is not evaluable and the participant is receiving continuous bladder irrigation, has nephrostomy tubes that are uncapped, or the urine is visually bloody, macroscopic hematuria is considered unresolved. For all other Bedi assessments where the grade is not evaluable, the grade is considered missing.

The analysis date for a Bedi assessment is the visual assessment date. If there is no visual assessment date, the urine collection date will be used. Otherwise, the visit date will be used. One Bedi assessment will be selected per analysis date. If there are multiple Bedi assessments on the same analysis date, the worst case is selected. If for a visit, there are Bedi assessments with a visual assessment date or urine collection date, assessments with only a visit date will not be selected.

If there are multiple Hemostick scores on the same date, the highest score will be selected.

If the result of the primary efficacy endpoint (ie, time to resolution of macroscopic hematuria) is statistically significant based on the BK ITT Population, a formal hypothesis test will be conducted sequentially of this same endpoint based on the overall ITT Population using a one-sided 0.025 significance level.

A sensitivity analysis of the primary efficacy endpoint will also be conducted for the BK ITT population, using a Cox proportional hazards model in order to account for additional potential confounders of the treatment effect. In addition, supportive analyses of the primary efficacy endpoint will also be performed based on the BK mITT, BK PP and mITT Populations.

Primary efficacy endpoint in the estimand framework is described as follows:

Statistical category	Estimand: Treatment: Study Treatment (PSL) or Placebo				
	Population: Pediatric and adult participants with virus-associated hemorrhagic cystitis				
	following allogeneic HCT				
	documented E to Grade 0 or visual urine as nephrostomy capped, Bedi resolution.	Endpoint (Variable): Time to resolution of macroscopic hematuria in participants with documented BK viruria. Resolution of macroscopic hematuria is defined as resolution to Grade 0 or 1 on the Bedi scale as assessed by the Investigator on 2 consecutive visual urine assessments ≥2 days apart without continuous bladder irrigation or nephrostomy tubes that are uncapped. If a participant has nephrostomy tubes that are capped, Bedi assessments may be performed, for the purpose of assessing for resolution			
	Population-le	evel summary: Median time to resolution of ma	acroscopic hematuria.		
	Intercurrent e	events (ICE):			
	1. Use o 2. Early	f definitive therapies to stop bladder bleeding discontinuation from the study treatment before	e achieving resolution		
	3. Death	due to any cause before achieving resolution	To before achieving		
	resolu	ition	is before achieving		
	Analysis set	Intercurrent event handling strategy	Population-level summary (Analysis):		
Primary	BK ITT	 Composite strategy: Participants with ICE 1 will be considered treatment failures for the primary endpoint of time to resolution of macroscopic hematuria and will be censored at the last follow- up time of any participant. Treatment policy strategy: Data collected after occurrence of ICE 2 will be used for the primary endpoint. Composite strategy: Participants with ICE 3 will be censored at the last follow-up time of any participants. Composite strategy: Participants with ICE 4 will be considered treatment failures for the primary endpoint of time to resolution of macroscopic hematuria and will be censored at the last follow- up time of any participant. 	Treatment comparison using a stratified log-rank test (by stratification factors at randomization)		
Sensitivity Analysis	BK ITT	Same as primary	A stratified Cox model including fixed effect terms for randomized treatment assignment, concomitant antiviral use, and concomitant systemic corticosteroid use.		
Supportive 1	BK mITT	Same as primary	Same as primary		
Supportive 2	BK PP	Same as primary	Same as primary		
Supportive 3	mITT	Same as primary	Same as primary		

Subgroup analyses will be conducted for the BK ITT population to compare the primary endpoint by baseline BKV viruria (<10⁷ copies/mL vs \geq 10⁷ copies/mL), demographic characteristics (eg, age group, sex), stratification factors (derived based on EDC data), and use of concomitant antiviral therapies with potential activity against BK virus during the study. Such agents include cidofovir, ciprofloxacin, and leflunomide. The subgroup analysis will also be conducted by the number of HLA matches and class of HLA matches (class I/II/both).

Analysis will be performed excluding participants who did not have a Bedi Grade ≥2 at randomization from the BK ITT and BK mITT.

All the time to event primary efficacy endpoints will be presented using Kaplan-Meier plots. The estimated median time to event with the corresponding 95% confidence intervals will be presented by treatment group.

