Participants randomized to the PSL arm will receive separate infusions of partially HLA -matched PSL cells (each administered via central or peripheral intravenous [IV] infusion over approximately minutes as a slow push).

The placebo arm will receive separate IV infusions of cryopreservation media (without cells).

The second infusion (PSL or placebo) will occur approximately (± 3) days after the first infusion. Administering the second infusion as early as feasible within this window is encouraged. Participants who weigh <40 kg at the time of screening will receive PSL cells

(or placebo), while participants who weigh ≥40 kg at the time of screening will receive PSL cells (or placebo).

EFFICACY VARIABLES:

Primary Efficacy Endpoint

The primary endpoint is the time to resolution of macroscopic hematuria in participants with documented BK viruria. A supplementary analysis will evaluate the time to resolution of macroscopic hematuria in participants with any virus-associated HC. Resolution of macroscopic hematuria is defined as resolution to Grade 0 or 1 on the Bedi scale as assessed by the Investigator on 2 consecutive visual urine assessments >2 days apart without continuous bladder irrigation or nephrostomy tubes. However, if a participant has nephrostomy tubes that are capped, Bedi assessments may be performed, including for the purpose of assessing for resolution. A healthcare provider (HCP) on the study team (including a home health provider) may perform the visual urine assessment, but it is the Investigator's responsibility to determine the Bedi score. Grade 0 requires no detectable blood by urinalysis; Grade 1 hematuria requires confirmation of resolution by urinalysis results of ≤ 100 RBCs/high power field (HPF). Time to resolution will be calculated starting from the date of randomization. The second urine assessment is required to establish resolution, but for the calculation of time to resolution, the date of the first of these two visual urine assessments without macroscopic hematuria (by the Hemostick® visual scale for outpatients; by the Bedi scale for inpatients) will be used. Participants will be followed for the primary endpoint for a maximum of 24 weeks from the date of randomization.

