7.1.3 Hemostick® Visual Scale for Outpatients

The Hemostick is a printed visual scale with 6 color fields that standardizes the characterization of macroscopic hematuria severity. The numbering of the Hemostick scale does not map directly to the Bedi grade. The Hemostick will be used as a monitoring tool for outpatients. A Hemostick score of 0 or 1 will trigger two hematuria visual assessments with Bedi grading by an HCP on the study team, each with an accompanying urinalysis; these assessments will be used to confirm resolution of macroscopic hematuria. Similarly, following resolution of macroscopic hematuria, Hemostick assessments will be used for outpatients to monitor for potential relapse. Participants, caregivers, and home health providers (if needed) will be trained to use and interpret the Hemostick in the outpatient setting via an instruction manual. For an image of the Hemostick visual scale, please visit https://hemostick.com/engelska/picture.

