7.1.5 Urine Visual Assessment to Confirm Resolution of Macroscopic Hematuria

Resolution of macroscopic hematuria is defined as resolution to Grade 0 or 1 on the Bedi scale⁴⁷ on 2 consecutive visual urine assessments ≥ 2 days apart without continuous bladder irrigation or nephrostomy tubes; Grade 1 hematuria requires confirmation of resolution by urinalysis results of ≤ 100 RBCs/HPF. If a participant has nephrostomy tubes that are capped, Bedi assessments may be performed, including for the purpose of assessing for resolution.

For inpatients, if absence of macroscopic hematuria is confirmed using the Bedi scale with urinalysis, the resolution date will be considered the date of the first of these 2 consecutive visual urine assessments.

For outpatients, the earliest date of visual assessment without macroscopic hematuria (Hemostick value of 0 or 1) will trigger 2 laboratory urinalysis assessments ≥2 days apart to confirm the resolution of macroscopic hematuria. If absence of macroscopic hematuria is confirmed on

urinalysis (≤100 RBCs/HPF), the resolution date will be considered the first date of visual assessment without macroscopic hematuria using the Hemostick.

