	Resolved	Bedi assessment with U/A 1 × per week	Bedi assessment with U/A 1 × per week	
Outpatient	Unresolved	Hemostick daily; Bedi assessment with U/A 1 × per week	Hemostick 2 × per week ≥2 days apart; Bedi assessment with U/A 1× per week	
	Resolved	Hemostick 1× per week; Bedi assessment with U/A 1 × per week	Hemostick 1 × per week; Bedi assessment with U/A at Week 12 and 24 study visits	

Table 1. Thume of visual Other Assessments with Otharysis	Table 1.	Timing of Visual	Urine Assessments	with Urinalysis
---	----------	------------------	--------------------------	-----------------

[1] Resolved macroscopic hematuria is defined as resolution to Grade 0 or 1 on the Bedi scale as assessed by an HCP on the study team on 2 consecutive visual urine assessments ≥2 days apart without continuous bladder irrigation or nephrostomy tubes that are uncapped. However, if a participant has nephrostomy tubes that are capped, Bedi assessments may be performed on urine voided through the urethra or a bladder catheter (eg, Foley or suprapubic catheter), including for the purpose of assessing for resolution. Abbreviations: HCP = healthcare provider; U/A = urinalysis

In support of the key secondary objective, bladder pain will be assessed using age-appropriate COAs.

Participants will also have urine and blood samples sent at prespecified intervals during the study to monitor viral loads of all the viruses targeted by PSL (BKV, AdV, CMV, HHV-6, JCV, and EBV). For participants who develop symptoms and/or signs of possible virus-associated gastrointestinal disease, and whose treating physician determines that laboratory evaluation of stool specimens for diagnostic and/or monitoring reasons is clinically indicated, stool samples for AdV and CMV viral load determination should, when possible, be sent to the central laboratory. Similarly, for participants who develop symptoms and/or signs of possible virus-associated neurological disease, and whose treating physician determines that laboratory evaluation of cerebrospinal fluid (CSF) for diagnostic and/or monitoring reasons is clinically indicated, CSF samples for CMV, HHV-6, and JCV viral load determination should, when possible, be sent to the central laboratory. Be sent to the central laboratory evaluation of cerebrospinal fluid (CSF) for diagnostic and/or monitoring reasons is clinically indicated, csF samples for CMV, HHV-6, and JCV viral load determination should, when possible, be sent to the central laboratory.

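### The SAP dates outpatient resolution by a Hemostick of 0, the protocol by 0 or 1, and no SAP rule dates a confirmed outpatient who scores 1

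*SAP*

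**What the plan says.** **Protocol.** Section 7.1.3 states: "A Hemostick score of 0 or 1 will trigger two hematuria visual assessments with Bedi grading by an HCP on the study team". Section 7.1.5 repeats the threshold for outpatients: "the earliest date of visual assessment without macroscopic hematuria (Hemostick value of 0 or 1) will trigger 2 laboratory urinalysis assessments". If those assessments confirm, "the resolution date will be considered the first date of visual assessment without macroscopic hematuria using the Hemostick". The Synopsis (Primary Efficacy Endpoint) also anchors the date to the confirming assessments, using "the date of the first of these two visual urine assessments without macroscopic hematuria".

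**SAP 3.4.1.** The event is dated at the first visual assessment without macroscopic hematuria, judged "by the Hemostick® visual scale with score of 0 for outpatients; by the Bedi scale with a Grade 0 or 1 for inpatients". The same sentence adds that "2 consecutive Bedi grades of 0 or 1 are required to establish resolution as noted above". There is one fallback: "If an outpatient does not have a Hemostick score at the time of resolution, the first of the 2 consecutive Bedi grades" supplies the date. For an inpatient who resolves on the day of discharge and has no Bedi grade then, the Hemostick score is used, with no threshold given. If several Hemostick scores fall on one date, the highest counts.

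**Assessment frequency (SAP Table 1).** An unresolved outpatient reads the Hemostick daily through Week 6 and twice weekly afterwards. A resolved outpatient through Week 6 has "Hemostick 1× per week; Bedi assessment with U/A 1 × per week", and the Hemostick stays weekly after that.

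**The concern.** The two documents give different thresholds for the date of the primary event, and the SAP does not present its threshold as a change. It does explain another departure from the protocol, the numbering of study days (SAP 3.1.2). The protocol can date an outpatient who triggers on a 1. The SAP cannot, unless a 0 follows. Its fallback does not help, because a score of 1 is a score.

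The SAP also states the first clear assessment and the required Bedi pair side by side, with no window, order or condition on bleeding in between.

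The date enters the primary log-rank test, the hazard ratio and the median time to resolution, which is the estimand's summary measure (SAP 3.4.1). It also enters the futility look (SAP 3.7) and starts the clock for time to recurrence (SAP 3.4.3). Two careful programmers could build different primary datasets from this text. Choosing between them after unblinding would be a post hoc decision on the primary endpoint.

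**Working it through.** **1. The rules side by side**

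| Confirmed outpatient | Protocol 7.1.5 | SAP 3.4.1 |
|---|---|---|
| Hemostick 0 leads into the pair | date of that 0 | date of that 0 |
| Hemostick 1 leads into the pair, 0 recorded later | date of the 1 | date of the later 0 |
| Hemostick 1, no 0 ever recorded | date of the 1 | not defined |
| No Hemostick score at resolution | not addressed | first Bedi of the pair |

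**2. A hypothetical case.** Hemostick 1 on Day 20, Bedi 0 or 1 on Days 21 and 24.
- Protocol: Day 20.
- An inpatient with the same Bedi grades, under the SAP: Day 21.
- Outpatient under the SAP: the first 0. Readings stay daily until the pair is complete, so a 0 by Day 24 costs only a few days. After Day 24 readings are weekly, so the next scheduled one can be as late as 24 + 7 = Day 31. That is 11 days after the protocol's date and later than both assessments that established resolution. If readings stay at 1, there is no date.

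**3. The plan's own power.** Inputs from SAP 2.2.3: 105 BK ITT participants, medians 12 and 6 weeks, 24 weeks of follow-up, 20% exponential dropout, one-sided 0.025. The allocation ratio is redacted, so 1:1 and 2:1 were both tried.
- λ = ln 2/12 and ln 2/6 per week; g = −ln(0.8)/24.
- P(event) = λ/(λ+g) × [1 − exp(−24(λ+g))] = 0.689 (placebo) and 0.879 (PSL).
- Events at 1:1: 105 × (0.689 + 0.879)/2 = 82.3. Power by Schoenfeld: Φ(√(82.3 × 0.25) × ln 2 − 1.96) = 88.2%.
- Events at 2:1: 85.7. Power: Φ(√(85.7 × 2/9) × ln 2 − 1.96) = 85.6%.

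The SAP states 86.4%; both results are within 2 points of it. The formula takes no input on event dating, so it neither shows the problem nor changes with the fix.

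**4. Illustrative size by simulated log-rank tests.** Assumptions not in the documents: 50% outpatients and the same pattern of date errors in both arms. The Monte Carlo standard error is under 1 point. Delays were exponential and applied to every outpatient, not only those scoring 1, and a delayed date beyond follow-up was censored. Early zeros were placed uniformly before the true resolution.

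| Scenario | 1:1 | 2:1 |
|---|---|---|
| Correct dates | 88.1% | 82.9% |
| Mean delay 1, 2, 4 weeks | 87.4, 86.6, 83.0% | 82.8, 81.1, 77.8% |
| Isolated early 0 in 10, 30, 50% of outpatients | 87.1, 86.3, 85.6% | 83.5, 82.8, 82.3% |

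A harsher case, isolated zeros at 5% per day, gives about 80% at 1:1. At that rate 1 − 0.95^42 = 88% of outpatients still unresolved through Week 6 would have shown a spurious zero.

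**5. What happens to undated responders.** In a separate run (1:1, 50% outpatients, baseline 87.9%), 30 to 50% of outpatients triggered on a 1, the first 0 came on average 3 weeks later, and 30% of these never recorded one.
- Undated responders censored: 80 to 73%.
- Undated or overrun cases given the first Bedi date: 88.3 to 87.6%.
- Censoring alone, with no delay: 80 to 74%.

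The loss in that scenario comes almost entirely from the censoring.

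**The case against.** **The 0-only rule may be deliberate.** The SAP is the later and more detailed document, and a stricter threshold makes false early dates less likely. That is fair, but a deliberate change should be stated as one, and it would still need a rule for a score of 1.

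**A reader might infer a power loss to somewhere near 73 to 80%.** The documents do not support this. It needs confirmed responders to be censored for want of a Hemostick 0. SAP 3.4.1 establishes resolution by the Bedi pair and censors those not observed to resolve; it does not say that a confirmed but undated participant is censored. An average delay of 3 weeks is also unsupported, because Hemostick readings become weekly only once the pair is complete.

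**A reader might infer that the SAP backdates events to any stray zero.** That takes a very literal reading. The same sentence requires the Bedi pair, the fallback looks for a score at the time of resolution, and protocol 7.1.5 makes the date depend on confirmation. What stands is that the SAP leaves the time of resolution undefined, so a literal program could do it. The gap is not unique to the SAP: protocol 7.1.1 is just as loose, though the Synopsis and 7.1.5 tie it down.

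**A reader might infer bias between arms or a raised false-positive rate.** The trial is double-blind, and bias would need the outpatient share or the Hemostick pattern to differ by arm, which nothing in the documents shows. With a 12-week median in both arms, one-sided rejection was 2.6% (late or undated) and 2.4% (early zeros), against 2.4% at baseline.

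**Conclusion.** The point holds as a conflict between two stated rules for the primary event date, with a case that the SAP does not cover: a confirmed outpatient whose Hemostick is 1. The missing express link to the Bedi pair is a secondary drafting gap.

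The effect on power cannot be computed from the documents. Under the assumptions above (1:1, 50% outpatients, equal patterns in both arms) it runs from nothing detectable to about 5 points (88.1% to 83.0%, at a mean delay of 4 weeks in all outpatients). It reaches about 8 points only with isolated zeros at an extreme daily rate. At 2:1 early zeros show no detectable effect, and the 4-week delay costs about 5 points (82.9% to 77.8%).

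The case for correction rests on having one reproducible event date, since the same date feeds the hazard ratio, the median, the futility look and time to recurrence. It should be fixed before anyone derives the endpoint on unblinded data, but it does not by itself put the primary test in doubt.

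**What to change.** Use one derivation in both documents:

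1. Agree a single Hemostick threshold. If the SAP keeps 0, state and justify it as a departure from the protocol's 0 or 1.
2. Identify the confirming Bedi pair first.
3. Date an outpatient event at the earliest qualifying Hemostick leading into that pair with no macroscopic hematuria in between, and never later than the first Bedi of the pair.
4. If no Hemostick qualifies, whether because it is missing or because the score is above the threshold, use the first Bedi date.
5. Apply the same threshold to the discharge-day rule.

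A shorter repair, stating the threshold and extending the existing Bedi fallback to scores above it, would close the undated case but leave the link to the pair implicit.

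The cost is a few sentences in the SAP, a matching protocol clarification if the threshold changes, and derivation code. All the readings needed are already collected.
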